3.2 Exclusion Criteria

Exclusion criteria	
 • Those patients unwilling to participate, those unable to understand sufficiently to give informed consent and those unable to participate due to the severity of COVID-19 disease. • Those not classified as of either South Asian or White British heritage. • Patients with malignancy, who are pregnant, on long term immune suppression, or unable to give informed consent due to inability to communicate in, understand or read English • Those who are not willing to have an oral examination, or donate blood or saliva samples. • Those who cannot chew / drool to provide a SWMF sample due to severe/critical conditions. • Participation in other current research that is designed to, or is expected to alter the immune response. • Diabetes not excluded but screening for diabetes will be performed: glucose will be assessed in blood/serum sample (150ul).
--------------------	--

3.3 Criteria for Premature Withdrawal

- If subjects withdraw consent
- Patients no longer wanting to continue with study

Participants have the right to withdraw from the study at any time for any reason.

4. Study procedures

4.1 Informed Consent Procedures

Participant Information Sheets will be given at the first point of contact regarding the study. For GSTT patients and volunteer participants in PIC sites this will normally be the clinical team. For volunteer participants responding to invitations to participate, this will normally be the clinical research dentist. Potential participants will be given a participant information sheet, and the research will be clearly explained verbally.

The participants will be given a minimum of 30 minutes to provide consent after discussion of the study. If any participants require a longer period of time to make a decision, this will be arranged.

If in the sequential part of the study a participant decides not to continue, samples and data that has already been collected will be included unless the participant specifically tell us not to.

4.2 Screening Procedures

Within GSTT, there is a dedicated COVID research team including nurses and consultants in infection, consultants in intensive care who have indicated willingness to help identify suitable patients meeting the inclusion criteria. Voluntary participation in the research project will be emphasized. Clinical care will continue as normal if the participant decides to leave the research at any time. Verbal and written consent will be obtained at the second visit by a member of the research team. Volunteers will be recruited from staff at GSTT and KCL through advertisement and Participant Identification Centers will be opened to advertise the study locally.

4.3 Randomisation Procedures

Samples will not be randomized.

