2.1. Trial Objectives

- Primary Objective

The key aim of this research in South Asian populations and White British populations, is to find out whether differences in COVID-19 morbidity and mortality in similar populations in the UK might be related to mucosal immunity expressed in the mouth and to the oral microbiome (the total bacteria, fungi and viruses living in the mouth). This will be achieved by determining

whether in the mouth there are differences between the participant groups of mucosal natural immunity (innate immunity), immune responses to SARS-COV2 antigens (adaptive immunity), or the oral microbiome

- Secondary Objectives

1. To determine whether differences in mucosal immunity or differences in the oral microbiome correlate with susceptibility to COVID-19 infection, or to progression and recovery from the disease.

2. To determine whether the presence of pre-existing oral disease is related to susceptibility to SARS-CoV2 infection, to severity of COVID-19 disease or relates to the nature of mucosal immunity and to the composition and activity of the oral microbiome

- Primary End Point

- Collection, processing and analysis of samples. Statistically significant quantitative differences in measured mucosal innate immune factors, mucosal adaptive immune factors and/or in the oral microbiome in relation to 1) a comparison between South Asian and White British populations in the UK 2) the degree of severity of COVID in South Asian and White British participants in the UK

- Secondary End point

- Generation of raw data.
- *a comparison between South Asian populations in the UK and in Chennai, India.

**Note: This is the UK part of an international research collaboration between the UK (funded by the MRC) and India (funded by the DBT) with research being carried out separately but in parallel in the two Countries and generating results which will be directly compared.*

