Each of the two population cohorts (South Asian and White British) has four sub-groups (clinically uninfected subjects, asymptomatic/mild, symptomatic moderate/severe, and recovered). After patient information sheets and consent, then oral health questionnaires (5mins), SWMF samples (5-15 mins), oral health (periodontal) examination (10 mins), and blood via venesection (5 mins). Patients will chew on a pellet of wax until approximately 4ml SWMF is recovered by drooling into sterile universal containers (between 5 and 10 minutes normally) after which the chewed wax will be wrapped in gauze and disposed with other clinical waste in adherence to infection control procedures. Blood samples may be taken before, during or after the SWMF collection. Repeat blood and stimulated SWMF will be taken at approximately 2 weeks, 4 weeks and 12 weeks after baseline for those participants willing to take part in the sequential studies. Oral examination and partial mouth recording will not be repeated unless any material change in oral condition is evident.

Uninfected subjects will be further defined as those who do not show antibodies to nuclear capsid protein antigens. The presence of such antibodies would indicate exposure to SARS-CoV2 rather than immunisation, and would be classified as asymptomatic if no history of symptoms.

Number of samples: With South Asian and White British participants, there will be up to 100 patient samples in each of the four sub-groups (uninfected subjects, asymptomatic/mild and moderate/severe disease, and recovered.). All will be assayed for immunological parameters, and the first 50 in each group for microbiome analysis, with the remainder stored for future analysis. The first 50 participants in each group will be invited to provide sequential samples.

Times of samples: There will be repeat samples of SWMF and blood at approximately 2, 4 and 12 weeks. Those SWMF at 4 weeks will be analysed for the microbiome in addition to the immunology (see table 1).

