Timing of research: We have recognised that the success of vaccination in the UK has reduced the potential patient pool, although the Omicron strain has produced a surge in cases. Samples will be taken over 15 months and may include a greater proportion of ambulant patients than originally planned, including those identified as asymptomatic carriers from routine testing, and those to be vaccinated. Although samples will be batch analysed, we do not anticipate that robust data can be determined until towards the end of the collection period, and then compared with the data derived from the study in Chennai. Findings will be disseminated as widely as possible in academic journals, academic meetings and in appropriate form in public media and a study website.

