4.4 Schedule of Treatment for each visit

Please see section 2.2 trial design. There is no treatment involved in this study.

Patients having been identified by the clinical treatment team as being suitable for recruitment to the study, will be asked whether they would like to participate in the study and given a participant information sheet (PIS) by the clinical team providing their care. The patient will be given at least 30 minutes to read and decide whether they would like to proceed to attend the pre-sampling visit. Patients who do not wish to participate will receive standard clinical care as normal. Volunteers also will be provided the PIS and have at least 30 mins to read through before providing informed consent.

After the patient information sheet has been given and consent obtained, the medical and oral health questionnaires will be asked, followed by the collection of SWMF (5-15 mins). Patients will chew on a pellet of wax until approximately 4ml SWMF is recovered by drooling into sterile universal containers (normally 5-10 minutes). The chewed wax will be wrapped in gauze and disposed with other clinical waste in adherence to infection control procedures. The oral health examination (10 minutes) will take place. Blood samples total 15ml (approximately 5 minutes) may be taken before, during or after the SWMF collection. Ward visits and follow up visits of patients previously seen at GSTT will be recorded in patients' hospital notes using EPR. For volunteer ambulant participants not previously patients of GSTT, appointments will be made at Guys Dental Hospital and patients pre-registered. Visits will be recorded on EPR and SALUD. Each participant in the three infected sub-groups (mild, moderate, recovered) once enrolled in the study, and willing to participate in the sequential part, would have a total participation time of approximately 85 minutes and four visits over 12 weeks. Uninfected subjects would be either a single visit of 40 mins or 60 minutes with a follow-up visit at four weeks (but not including travelling time)

Oral Health Clinical Assessment

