5.1 Central/Local Laboratories

Blood samples designated for routine blood tests and glucose will be sent to the hospital blood pathology lab for processing and analysis according to routine processes.

The remaining blood samples will be processed and prepared in the Centre for Host Microbiome laboratory on [name], Guy’s Hospital. Microbial DNA extraction will be performed in these laboratories. Extracted microbial DNA identified by study number only will be sequenced by specialised commercial companies or academic institutions in the UK or non UK.

The salivary microbiome will be analysed on 50-100 patients per group after microbial DNA extraction with standardised protocol, using shotgun metagenomic sequencing on an Illumina NovoSeq generating > 20 million reads/sample. Sequencing will be performed by a commercial provider. Analysis of the sequencing data will be performed at KCL under the supervision of CHMI academics as described in section 2.4. The salivary metabolome will be determined using NMR. The longitudinal immune response and shifts in the oral microbiota will be correlated with COVID-19 severity as well as both COVID-19 and non-COVID-19 oral disease. We will identify significant differences in oral microbiota & immune responses during transition from viral to immunological to post-COVID-19 phases, identifying specific host factors as therapeutic targets.

Salivary secretory IgA antibody assay to study mucosal responses to antigens associated with COVID-19.

SARS is a closely related virus to SARS-CoV2. Several crystal structures have been published that describe how different antigens recognize the SARS spike protein receptor binding domain. These highlighted antigenic regions in the SARS spike protein. Structures are also now available for the homologous SARS-CoV2 spike protein receptor binding domain. The amino acid sequence of the spike protein from SARS & SARS-CoV2 were compared. Major differences were identified and 10 peptides constructed. Three of these have been selected and will be assayed by ELISA along with Capsid antigens obtained commercially. The group has extensive experience with ELISA techniques, and has performed preliminary experiments to verify their use in SWMF. (This kit has been developed and validated in King's College London, and methodology shared with VHS, Chennai for sample testing.)

Blood and SWMF lymphocyte phenotyping

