5.4 Sample Storage Procedures (if applicable)

All samples will be stored in an HTA licensed -80°C freezer until ready for testing. DNA extracted from samples will be stored in an HTA licensed -80°C freezer until ready for sequencing. (Designated Individual [name], HTA License number 12521, Person Designate: [name])

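### Samples are batch analysed with no stated balancing, so batch may be confounded with clinical group in the UK, and the direct UK–Chennai comparison cannot separate country from laboratory

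*Protocol*

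**What the plan says.** **Within the UK.**
- Section 4.3 (Randomisation Procedures) consists of one sentence: "Samples will not be randomized". Section 4.4, which follows, notes "There is no treatment involved in this study".
- Section 2.2 (Timing of research) says "Although samples will be batch analysed". Collection runs for 15 months and "may include a greater proportion of ambulant patients than originally planned".
- Section 2.2 (Number of samples) assigns "the first 50 in each group for microbiome analysis, with the remainder stored for future analysis".
- Section 5.1 allows more than one sequencing provider: extracted DNA "will be sequenced by specialised commercial companies or academic institutions in the UK or non UK".
- Section 5.4 says "All samples will be stored in an HTA licensed -80°C freezer until ready for testing".
- The group tests in sections 2.4 and 5.5 are Mann–Whitney, Kruskal–Wallis with Dunn, and Wilcoxon with Benjamini–Hochberg correction. None is described with a batch or laboratory term.

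**UK and Chennai.** Section 2.1 lists the comparison of South Asian populations in the two countries under the secondary end point, with "research being carried out separately but in parallel in the two Countries and generating results which will be directly compared". Two controls are stated. Section 5.5 matches participants on age and disease, and section 5.1 says the method of the salivary antibody ELISA was shared with Chennai.

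**The concern.** Assay readings shift between DNA extraction runs, sequencing runs, ELISA plates and bead-array kits. If groups are spread evenly over batches, such a shift adds noise only. If they are not, part of the shift appears as a group difference. The protocol supplies several conditions under which groups could be unevenly spread: batch analysis, a long collection with a changing case mix, a microbiome set chosen by order of recruitment, and possibly several sequencing providers. It also contains a sentence that can be read as ruling out the usual safeguard. The contrasts at stake are those of the primary end point, above all severity.

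The Chennai comparison has a structural problem. Where each side runs its own assays, the laboratory offset enters the country difference in full. Matching participants does not touch it, and multiplicity correction does not remove a bias.

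**Working it through.** **1. The plan's own figure.** Section 2.4 asks for 30 to 50 values per parameter. It gives no effect size, SD, alpha or power, so the figure cannot be reproduced. Under an assumed two-sided alpha of 0.05 and 80% power, the detectable difference is (1.960 + 0.842) × √(2/n): 0.72 SD at n = 30, 0.56 SD at n = 50 and 0.40 SD at n = 100. This gives a scale for the offsets below.

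**2. Batch and group within the UK.** Take two batches that differ by b SD. A share q of one group, and 1 − q of the other, lies in the first batch.
- Bias = b × (2q − 1).
- With no biological difference and SE = √(2/n), the two-sided rejection rate is Φ(bias/SE − 1.96) + Φ(−bias/SE − 1.96).
- SE = 0.200 at n = 50 and 0.141 at n = 100, the minimum and maximum cross-sectional group sizes in section 2.4.

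The documents give neither b nor q, so both are assumptions.

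| Split | b (SD) | Bias (SD) | n = 50 | n = 100 |
|---|---|---|---|---|
| 50/50 | any | 0 | about 5% | about 5% |
| 60/40 | 0.3–0.5 | 0.06–0.10 | 6–8% | 7–11% |
| 75/25 | 0.3–0.5 | 0.15–0.25 | 12–24% | 19–42% |
| 90/10 | 0.3–0.5 | 0.24–0.40 | 22–52% | 40–81% |

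Worked example, 75/25 with b = 0.5 at n = 50: bias = 0.5 × 0.5 = 0.25, and 0.25/0.200 = 1.25. Then Φ(1.25 − 1.96) + Φ(−1.25 − 1.96) = 0.239 + 0.001 = 0.24. The formula ignores the small extra within-group spread that the batches cause, which lowers these figures slightly.

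**3. Country and laboratory.** If each country assays its own samples, the country and laboratory indicators are the same column. A model with intercept, country and laboratory then has rank 2 with 3 parameters. Only the sum of the two effects can be estimated, and no analysis of those data can split it.

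With no true difference, the whole laboratory offset is bias. The offsets are assumed. So are the numbers per side, since the protocol gives no Chennai sample size.

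| Laboratory offset (SD) | 50 per side | 100 per side |
|---|---|---|
| 0.2 | 17% | 29% |
| 0.3 | 32% | 56% |
| 0.5 | 71% | 94% |

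A Mann–Whitney simulation with 4,000 replicates gave 16, 30 and 68% at 50 per side, and 26, 53 and 94% at 100.

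**4. What within-country contrasts achieve.** Write a group mean in Chennai as its true mean plus a laboratory offset L. Infected minus uninfected within Chennai is then free of L, because L is added to both terms. The same holds for log ratios when the offset is multiplicative. It does not hold if the laboratories differ in detection limit or in slope.

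**The case against.** The strongest reply is that section 4.3 answers a standard heading for an observational study. There is no treatment to allocate, so the sentence may mean only that nobody is randomly allocated. This stands: the sentence is ambiguous, and assay order, plates and runs are not mentioned there.

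Next, the composition of batches is not stated. Arrival-order batches appear nowhere, and the rule on the first 50 governs selection, not batching. Frozen storage, and the expectation in section 2.2 that robust data will come only towards the end of collection, fit late and well-mixed batches equally well. South Asian and White British participants are recruited by the same routes (section 3), and differing accrual by ethnicity is not stated. All of this stands. A reader might infer that batch is confounded with clinical group, including ethnicity. The documents do not support that; they support a risk, and mainly for severity.

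Plate layout may also sit in a laboratory manual, and a batch term in the statistical analysis plan. Neither document is shown, and their absence is not the point. The point is that section 4.3, read literally, rules out random assay order, and that section 2.1 itself commits to a direct comparison with Chennai.

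On Chennai, a reader might infer complete confounding for every assay. That is not stated either. UK DNA may be sequenced outside the UK, and the Chennai sequencing site is not given. Section 5.5 can also be read as comparing the analyses made within each country, which would be close to the remedy below. What remains is that no control across laboratories is stated beyond one ELISA method. A shared method reduces a laboratory offset for that assay but need not remove it, and it does nothing for cytokines, flow cytometry or metagenomes.

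**Conclusion.** The concern holds as a design weakness to be corrected, not as demonstrated bias.

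- **UK contrasts.** Confounding of batch with group is possible and unguarded as written. Its size depends wholly on the assumed offset and imbalance: none if batches are balanced, and false-positive rates of about 12–42% for a 75/25 split with offsets of 0.3–0.5 SD at 50 to 100 per group. Where groups overlap within batches and batch is recorded, adjustment in the analysis remains possible. If group and batch coincide, it does not.
- **UK–Chennai.** If each country runs its own assays, country and laboratory cannot be separated, whatever the sample size. The assumed offsets of 0.2–0.5 SD only show how readily this yields significant results: about 17–71% at 50 per side and 29–94% at 100. This concerns a secondary end point and leaves the primary UK comparisons untouched.

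**What to change.** **Section 4.3.** Reword along these lines: *Participants are not randomised. Stored frozen aliquots and DNA are assigned to extraction, sequencing and assay batches in random order, balanced over ethnicity and provisional clinical group at recruitment. A participant's serial samples go in one batch where storage allows. Each batch carries a blank and a pooled control, and batch is recorded.* The same balance should apply across sequencing providers.

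Two assays need their own rule:
- The nucleocapsid antibody assay helps to define who is uninfected (sections 2.2 and 3), so it can be balanced on recruitment category only.
- Where flow cytometry is run on fresh cells, record the run date and instrument controls.

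**Analysis.** A batch term does not fit into the planned unstratified rank tests. Use batch-stratified rank tests (for example van Elteren for two groups) or a regression with a batch term.

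**Chennai.** Replace the direct comparison in section 2.1 with a comparison of within-country contrasts, for example infected versus uninfected and severe versus mild. Treat differences in absolute level as descriptive unless a common calibrator or exchanged samples are run in both laboratories.

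**Cost.** A random list, a few control wells per batch, and some assays waiting until a batch is full. Frozen storage under section 5.4 makes this feasible. Without bridging material, absolute UK–India differences are not claimed.

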4.4 Schedule of Treatment for each visit

Please see section 2.2 trial design. There is no treatment involved in this study.

Patients having been identified by the clinical treatment team as being suitable for recruitment to the study, will be asked whether they would like to participate in the study and given a participant information sheet (PIS) by the clinical team providing their care. The patient will be given at least 30 minutes to read and decide whether they would like to proceed to attend the pre-sampling visit. Patients who do not wish to participate will receive standard clinical care as normal. Volunteers also will be provided the PIS and have at least 30 mins to read through before providing informed consent.

After the patient information sheet has been given and consent obtained, the medical and oral health questionnaires will be asked, followed by the collection of SWMF (5-15 mins). Patients will chew on a pellet of wax until approximately 4ml SWMF is recovered by drooling into sterile universal containers (normally 5-10 minutes). The chewed wax will be wrapped in gauze and disposed with other clinical waste in adherence to infection control procedures. The oral health examination (10 minutes) will take place. Blood samples total 15ml (approximately 5 minutes) may be taken before, during or after the SWMF collection. Ward visits and follow up visits of patients previously seen at GSTT will be recorded in patients' hospital notes using EPR. For volunteer ambulant participants not previously patients of GSTT, appointments will be made at Guys Dental Hospital and patients pre-registered. Visits will be recorded on EPR and SALUD. Each participant in the three infected sub-groups (mild, moderate, recovered) once enrolled in the study, and willing to participate in the sequential part, would have a total participation time of approximately 85 minutes and four visits over 12 weeks. Uninfected subjects would be either a single visit of 40 mins or 60 minutes with a follow-up visit at four weeks (but not including travelling time)

Oral Health Clinical Assessment

We wish to record the severity and extent of active inflammation of the periodontium: a situation where, cumulatively around the mouth, very large areas of eroded or ulcerated gingival sulcular and pocket epithelium may be present. The standard in the field is “PSR/BPE” – periodontal screening and recording/basic periodontal examination. We will record the deepest pocket on every standing tooth as an accurate cumulative measure of inflamed surface area using disposable, appropriately marked, WHO probes. PSR simplifies this to a single code per sextant.

